### Assessments and Evaluations:

*Baseline/Screening Evaluation:* For the single dose study, all subjects will undergo an outpatient screening evaluation to assess their eligibility prior to entrance into the study. A complete medical history and physical examination will be performed. Blood samples will be taken for a complete blood chemistry, blood counts, thyroid hormone panel and urinalysis. Subjects with impaired glucose tolerance or diabetes will be excluded. During baseline, subjects will be assessed for dietary intake data and instructed on weight maintenance diets. A taste (small sip) of the study product (30g) will also be administered during screening.

### Study Design of Ascending Single Dose

**Objective:** The Primary objective will be to assess the safety and tolerability of a single dose of the 5011-Nutrasorb in healthy subjects. Although this study is not designed to evaluate efficacy, we will assess the effect of a single dose of the botanical complex on glucose tolerance to determine if there is an acute effect.

**Design:** After all inclusion and exclusion criteria are met, subjects will be admitted to the inpatient unit of the Pennington Biomedical Research Center. After meeting inclusion and exclusion criteria, they will be randomized by the study statistician to receive a specific sequence of 3 treatments (3 doses of extract). Participants will be randomly assigned to

treatment sequences as this design balances order of treatment consumption with respect to the distribution of extraneous factors, known or unknown, that may potentially confound the association and assessment of botanical supplement use and carbohydrate metabolism. After baseline evaluation, subjects within each cohort will be randomized to one of 3 treatment sequences (order of receiving 2 doses of 5011-Nutrasorb and placebo based on the dosing plan outlined in **Table 1**). The statistician will prepare and give to the pharmacist a randomization schedule that is divided into 3 parts, one for each cohort. Nine treatment sequences will be indicated for each cohort in 3 permuted blocks of 3 treatment sequences where each treatment sequence appears exactly once in permuted block. This balances the use of treatment sequences throughout the duration of participants in the event that anticipated dose usage requires adjusting before completion of all treatment sequence assignments.

Figure 1: Single Ascending Dose Study														
Day of Study	Scr	-3	1	1	1	1	1	1	1	1	1	1	2	2
Hour of OGTT			-2	-1.5	-1	-0.5	0	1	2	4	10	12	22	24
Randomization			•											
Dosing	taste		•											
Vital Signs	•	•	•					•		•		•		•
Body Weight	•													•
Complete Blood Chemistry	•													•
Physical Exam	•													•
EKG	•									•				
OGTT a		•					•							
Adverse Event Assessment						•	•	•						•
Fasting Lipids	•													•
Insulin/Glucose b	•											•		•
Bioactives: Plasma		•	•	•	•	•	•	•	•	•	•			•

**Figure 1: Proposed Study Design Assessing Ascending Single Dose for each period in Table 1**

a OGTT will be conducted as described in Section 6.2 and will include assessment of insulin and glucose at -15 and 0 timepoints prior to ingestion of oral glucose load and at 30, 60, 90, 120 and 180 minutes post glucose load.

b Indicates insulin and glucose assessments conducted in addition to assessments as part of the OGTT

Parameters assessed as part of SAD study will consist of assessing safety with biochemical measures, and effect on insulin action (with use of HOMA-IR), and use of insulin response to glucose as assessed during oral glucose tolerance testing (OGTT) and with HOMA- $\square$ . The OGTT will be obtained at two time points, specifically at Day -3 (prior to randomization) and at Day 1. The protocol for OGTT in regard to timing of dosing of study intervention and for insulin/glucose assessments are summarized below;

- 1) **Day -3:** OGTT will be conducted according to the specific method as outlined in Section 6.2, entitled "Glucose Tolerance". Specifically, a 75-g oral glucose tolerance test will be used to assess for glucose tolerance and insulin secretory function according to the guidelines of the American Diabetes Association. Time points for assessment of insulin glucose will be at -15, 0, 30, 60, 90, 120, and 180 minutes.
- 2) **Day 1:** The subject will be given either the placebo or specified dose of the study intervention two hours prior to the OGTT. This time point on the figure is termed "-2 hours" and specified as "Hour of OGTT".

- 3) **Day 1:** At 1 hour and 45 minutes post study intervention dosing on Day 1 (corresponding to time point -15 minutes of the OGTT) and at two hours post study intervention dosing (corresponding to 0 time point of the OGTT), insulin and glucose levels will be obtained in the fasting state and will represent baseline labs for the OGTT. After obtaining the 0 time point baseline labs of the OGTT, 75 grams of oral glucose will be ingested. Repeat insulin and glucose levels will be obtained at 30, 60, 90, 120 and 180 minutes after glucose ingestion.
- 4) **Day 1:** To evaluate effect of extract dosing on insulin/glucose over time, repeat insulin and glucose level will be evaluated at 12 hours after the start of the OGTT. These levels are outlined in Figure 1
- 5) **Day 2:** To evaluate effect of extract dosing on insulin/glucose over time, repeat insulin and glucose levels will be evaluated at 24 hours after the start of the OGTT that was conducted on Day 1. These levels are outlined in Figure 1.

Fasting lipids will be obtained 24 hours after dosing. **Figure 1** outlines the schedule plan for metabolic testing in our single dose studies. We do not feel we need to alter any testing based on hormone/menstrual cycle issues that need to be timed, monitored, or controlled for with respect to the study outcomes.

**Assessing Botanical Levels/Compliance:** Levels of the bioactive components will be assessed by determining concentrations of the component in blood plasma (circulating levels) and urine (excretion) on inpatient days. Subjects will be given their randomized intervention (5011-Nutrasorb or placebo) at the -2.0 hour of OGTT (considered as 0 Hour of Bioactives) (see Table 2). Plasma will be obtained at the -2.0 hour of OGTT (i.e. 0 hours of Bioactive) then at -1.5, -1.0, -0.5, 0, 1, and 2 hour of OGTT. These time points labeled as "Hour of OGTT" correspond to the following time points for bioactive assessment [Labeled as "Hour of Bioactives"] as outlined in the Table 2 which occur as follows: 0, 0.5, 1, 1.5, 2, 3, and 4 hours post ingestion (Hour of Bioactive). Blood for bioactives will also be obtained at 6, 12 and 24 hours (hours of Bioactives) after extract or placebo ingestion corresponding to 4, 10 and 22 hours post OGTT ("Hour of OGTT") (see Table 2). After initial void, urine will be collected over the 6 hour interval (corresponding to 0 through hour 6 of "hour of bioactives"). These specimens will be assessed for bioactives in the Botanical Core lab.

Table 2: Correlation of Blood Draws for OGTT in relation to Bioactive Assessment Blood Draws

Day of Study	1	1	1	1	1	1	1	1	1	1	1	1	1	1	2	2
Hour of OGTT	-2	-1.5	-1	-0.5	-0.25	0	0.5	1	1.5	2	3	4	10	12	22	24
OGTT Draws					X	X	X	X	X	X	X			X		X
Hour of Bioactives	0	0.5	1	1.5	1.75	2	2.5	3	3.5	4	5	6	12	14	24	26
Bioactive Draws	X	X	X	X		X		X		X	X	X		X		X

#### **B. Phase 1 Studies: Multiple Oral Dose Evaluation**

**Objective:** The **primary objective** is to assess the safety and tolerability of multiple daily doses of the 5011-Nutrasorb complex in healthy subjects that include subjects whose phenotype as assessed by BMI are in the lean, overweight and obese categories. The

**secondary objective** is to assess the pharmacodynamic effect of multiple daily doses of the extract on glucose tolerance. We will evaluate other proposed mechanisms of action including assessment of insulin secretion with OGTTs, plasma lipid levels and plasma appearance of proposed metabolites.

Table 3. Multiple Oral Dose Randomization			
	Period 1	Period 2	Period 3
Cohort 1			
Sequence 1 (n=3)	D1	Placebo	D2
Sequence 2 (n=3)	D1	D2	Placebo
Sequence 3 (n=3)	Placebo	D1	D2
Cohort 2			
Sequence 4 (n=3)	D2	Placebo	D3
Sequence 5 (n=3)	D2	D3	Placebo
Sequence 6 (n=3)	Placebo	D2	D3
Cohort 3			
Sequence 7 (n=3)	D1	Placebo	D3
Sequence 8 (n=3)	D1	D3	Placebo
Sequence 9 (n=3)	Placebo	D1	D3

**Dosing:** Twenty Seven subjects (3 cohorts of 9 subjects with 3 subjects (1 normal weight, 1 overweight and 1 obese) randomly assigned to each of 3 treatment sequences) will participate in a three period crossover treatment regimen with each treatment period comprising once daily dosing for 21 days. Subjects will be randomly assigned to receive the treatments in the sequence orders shown in **Table 2**: 1) Cohort 1 will comprise 3 sequences of 3 treatments where placebo is dose 0 of 5011-Nutrasorb, D1 is a low dose (0.3 g) of 5011-Nutrasorb and D2 a medium dose (1 g) of 5011-Nutrasorb; 2) Cohort 2 will comprise 3 sequences of 3 treatments where D2 is a medium dose (1 g) of the 5011-Nutrasorb and D3 (30 g) a high dose of the 5011-Nutrasorb; and 3) Cohort 3 will comprise 3 sequences of 3 treatments where D1 is a low dose (0.3 g) of the 5011- Nutrasorb and D3 a high dose (30 g) of the 5011-Nutrasorb. Dosing for the MAD study was determined by data obtained in the SAD study as outlined above. Specifically, as outlined in Table 1, we will have data on PK studies, safety and tolerability, and biological response. In addition, based on information from the plasma appearance data and from assessment of biological response, consideration will be given to providing dosing on a BID or TID regimen. All doses used in this phase have been tested in the single-dose portion of the protocol. In the single dose protocol, there was no observed signal for toxicity, tolerability or other adverse events noted. The doses evaluated in the single dose study are spread among all 3 cohorts and no new dose is being introduced in this phase. Blinded analysis of the glucose tolerance will be on-going during the study and dose changes will be made if necessary. Additionally, as stated, if none of these doses show adequate glucose tolerance effects then an additional cohort may be added to investigate a twice daily or three times a day dose. In each treatment period a single dose of the 5011- Nutrasorb will be administered daily

from days 1 to 21. Complete biochemical and hematologic assessments to evaluate safety will be obtained in addition to clinical monitoring for adverse events.

#### **Assessments and Evaluations:**

**Baseline/Screening Evaluation:** All subjects will undergo an outpatient screening evaluation to assess their eligibility prior to entrance into the study. A complete medical history and physical examination will be performed. Blood samples will be taken for a complete blood chemistry, blood counts, thyroid hormone panel and urinalysis. Subjects with impaired glucose tolerance or diabetes will be excluded. During baseline, subjects will be assessed for dietary intake data and instructed on weight maintenance diets.

[figure not shown]
#### **Study Design of Multiple Ascending Dose**

**Subjects:** We will test safety, tolerability and metabolism in individuals with a wide range of BMIs representing lean, overweight and obese subjects.

**Design:** After meeting inclusion and exclusion criteria, subjects will be randomized by the study statistician to one of the treatment sequences within each subject's appropriate BMI stratum. Participants will be randomly assigned to treatment sequences as this design balances order of treatment consumption with respect to the distribution of extraneous factors, known or unknown, that may potentially confound the association and assessment of botanical supplement use and insulin sensitivity. After baseline evaluation, subjects will have an OGTT, insulin/glucose and effect on insulin action and response on Day -3. They will also have a baseline DXA. There will be three (3) study periods each evaluating exposure through 21 days (see **Figure 2**). At day 1, of each treatment period, subjects will be randomly assigned to treatment sequence based on the dosing scheme proposed in Table 2. Repeat insulin/glucose, safety labs, OGTT and fasting lipid profile will be assessed at 7, 14, and 21 days. Parameters assessed will consist of assessing safety with biochemical measures, bioactive metabolites and effect on insulin action (with use of HOMA-IR) and insulin response to glucose as assessed during OGTT and with use of HOMA- $\beta$ . Fasting lipids will be obtained at 7, 14 and 21 days of each treatment period. **Figure 2** outlines the schedule plan for metabolic testing in our multiple dose studies. We do not feel we need to alter any testing based on hormone/menstrual cycle issues that need to be timed, monitored, or controlled for with respect to the study outcomes.

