#### **Assessments and Evaluations:**

**Figure 2: Multiple Dose Study**

Day of Study	Scr	-3	1	3	7	10	14	17	21
Randomization			•						
Vital Signs/Body Weight	•	•	•	•	•	•	•	•	•
Complete Blood Chemistry	•				•		•		•
Physical Exam/EKG	•				•		•		•
OGTT		•			•		•		•
Plasma Metabolites					•		•		•
Insulin Secretory Assessment	•				•		•		•
Fasting Insulin/Glucose	•				•		•		•
Bioactives: Plasma/Excretion*					•		•		•
DXA		•							•
Adverse Event Assessment	•	•	•	•	•	•	•	•	•

**Figure 2: Proposed Study Design Assessing Multiple Dose Study for each Period.** There will be three study periods of assessment (see Table 2). SCR; Screening (only done in the first study period). A one day +/- visit window is allowed.

*\*NOTE Subjects will be given their intervention (low or high dose 5011-Nutrasorb or placebo) two hours prior to start of OGTT (0 hour) and will have plasma obtained at 0, 30 minutes, 1, 1.5, 2, 3, and 4 hours post ingestion. After initial void, urine will be collected over the 6 hour interval. These specimens will be measured in the Botanical Core lab. Note: Intervention will not be administered at Day -3 of each test period.*

**Baseline/Screening Evaluation:** All subjects will undergo an outpatient screening evaluation to assess their eligibility prior to entrance into the study. A complete medical history and physical examination will be performed. Blood samples will be taken for a complete blood chemistry, blood counts, thyroid hormone panel and urinalysis. Subjects with impaired glucose tolerance or diabetes will be excluded. During baseline, subjects will be assessed for dietary intake data and instructed on weight maintenance diets. A taste (small sip) of the study product will also be administered during screening.

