#### **Screening**

All screening evaluations to determine eligibility must be completed and reviewed by the individual providing medical supervision or Principal Investigator prior to study start. Generally, all labs to assess entry criteria must be completed no less than 10 days before subject enters study. Screening evaluations are outlined in **Figure 1**.

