### **6.2.2 Enrollment, Baseline, and/or Randomization**

#### **Enrollment and Baseline Assessments**

All subjects will undergo an outpatient screening evaluation to assess their eligibility prior to entrance into the study. After informed consent, the following procedures will be conducted:

- A complete medical history and physical examination will be performed.
- Blood samples will be taken for a complete blood chemistry, blood counts, thyroid hormone panel and urinalysis.
- Subjects with diabetes will be excluded.
- Subjects will be assessed for dietary intake data and instructed on weight maintenance diets.

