### **7.5 Follow-up for Adverse Events**

After the initial AE/SAE report is completed and sent, the investigator is required to proactively follow each subject at subsequent visits/contacts. As currently practiced, it is planned that all AEs and SAEs will be followed in clinic until: 1) resolution; 2) the condition stabilizes; 3) the event is otherwise explained; or 4) the subject is lost to follow-up.

Additional measurements and/or evaluations as may be indicated will be conducted by the investigator/research team in order to elucidate as fully as possible the nature and/or causality of the AE or SAE. These evaluations/measurements may include additional laboratory tests or investigations, histopathological examinations, consultation with other health care professionals or radiologic examinations. In the event that a subject dies during participation in the study or during a recognized follow-up period, the investigator will provide the IRB/DSMB with a copy of any post-mortem findings, including histopathology.

New or updated information will be recorded in the originally completed data collection tool. The investigator will submit any updated SAE data within the designated reporting time frames.

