##### **Stopping Rules**

Dosing within a cohort will be stopped and further dosing will be halted until unblinded safety information can be reviewed in the event that:

- A death occurs
- Two or more subjects experience the same SAE following administration of study drug.
- Two or more subjects in one dose panel experience the same severe drug-related AE following administration of study drug
- Based on AEs, laboratory findings, clinical findings or ECGs the Investigator or DSMB determine that review of pertinent safety information is required.

Dosing may only resume if, after review of safety information, both the Investigator, DSMB and IRB agree that it is safe to proceed.

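### In the multiple-dose study, Periods 2 and 3 start without a complete chemistry and blood-count panel taken off study product

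*Combined protocol and SAP*

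**What the plan says.** Section 3.B (Study Design of Multiple Ascending Dose) sets the laboratory schedule: "Repeat insulin/glucose, safety labs, OGTT and fasting lipid profile will be assessed at 7, 14, and 21 days". Figure 2, which applies to each of the three periods, agrees. Its complete blood chemistry row is marked at screening and on Days 7, 14 and 21, and is blank on Days -3, 1 and 3. The caption adds "SCR; Screening (only done in the first study period", so the screening panel is not repeated.

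Each period does have a visit off product before dosing. The Figure 2 note says "Intervention will not be administered at Day -3 of each test period". That visit carries vital signs and weight, an OGTT (so glucose and insulin), DXA and adverse event assessment, but no chemistry or blood counts. Day 1 carries randomization, vital signs and weight, and adverse event assessment.

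No other part of the plan adds a panel before dosing in these periods. The Dosing paragraph of 3.B promises biochemical and hematologic safety assessments but gives no time points. The statement that chemistry is obtained before and after dosing belongs to the single-dose study (3.A).

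Section 9.1 gives 21 days of once-daily dosing followed by a 7-day washout, with the lower extract dose always before the higher. Section 9.5.1 makes safety and tolerability, judged clinically and biochemically, the primary outcome.

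**The concern.** The OGTT, which serves secondary outcomes, has an off-product reference in every period. The laboratory panel, which serves the primary safety outcome, has one only before Period 1. Two consequences follow.

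First, a chemistry or blood-count change that first appears after the Day 21 sample is not looked for before the next treatment starts. Second, if the Day 7 panel of the new period is abnormal, the schedule cannot show whether the change arose in the interval off product or on the new treatment. Section 9.6 refers to change from baseline to follow-up without saying which baseline applies in Periods 2 and 3.

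Because doses ascend within each subject, every higher-dose period falls in Period 2 or 3, including every period of repeated 30 g dosing.

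**Working it through.** The plan states no figure on this point to reproduce. The check is a count of days and of treatment starts.

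**Inputs.** 21 dosing days plus 7 washout days per period (9.1). Panels on Days 7, 14 and 21 (3.B text and Figure 2). Visit window: "A one day +/- visit window is allowed" (Figure 2). Sequences and numbers from Table 3: 3 cohorts, 3 sequences each, 3 subjects per sequence. The 30 g dose is D3, used in Cohorts 2 and 3.

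**Day count.** With study day 1 as Period 1 Day 1, each period takes 21 + 7 = 28 days, so periods start on days 1, 29 and 57. For the step from Period 1 to Period 2:
- Day 21 panel to the new Day 1: 29 - 21 = 8 days (6-10 with one day either way at both ends).
- Day 7 of Period 2 is study day 35. Day 21 panel to that panel: 35 - 21 = 14 days (12-16 with windows), of which 7 are washout.
- Day -3 of Period 2 is study day 25 or 26, depending on whether a Day 0 is counted. It falls 25 - 21 = 4 or 26 - 21 = 5 days after the last dose (3-6 if that visit moves by a day), which is inside the washout of days 22-28.
- Day -3 to the Day 7 panel: 35 - 26 = 9 or 35 - 25 = 10 days.

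The step from Period 2 to Period 3 is identical.

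**Treatment starts.** Each cohort in Table 3 uses the same three orders, so each order has 3 × 3 = 9 subjects, of whom 6 are in the two cohorts with 30 g.

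| Order | Period 2 start | Period 3 start |
|---|---|---|
| Low, placebo, high | placebo after low (9) | high after placebo (9; 6 at 30 g) |
| Low, high, placebo | high after low (9; 6 at 30 g) | placebo after high (9) |
| Placebo, low, high | low after placebo (9) | high after low (9; 6 at 30 g) |

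- All starts of Periods 2 and 3: 6 × 9 = 54, out of 27 × 3 = 81 subject-periods.
- Starting placebo: 9 + 9 = 18. Starting extract: 54 - 18 = 36.
- Starting extract directly after a lower extract dose: 9 + 9 = 18, of which 6 + 6 = 12 at 30 g.
- Starting 30 g: 6 + 6 + 6 = 18, which is every 30 g period in the study.
- Starts directly after placebo: 9 + 9 = 18. There the preceding Day 21 panel was taken on soy protein without extract, so recovery from extract is a lesser issue.

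**Extra panels.** One at Day -3 of Periods 2 and 3: 27 × 2 = 54.

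**The case against.** The strongest reply is that the plan already watches laboratory safety closely. Every period has three panels, and the last can be reviewed before the next period starts. Vital signs and adverse events are checked on Day -3 and Day 1. A clinically significant laboratory abnormality is an adverse event (7.3), and under 7.5 "all AEs and SAEs will be followed in clinic until: 1) resolution", or until it stabilises, is explained or the subject is lost. Section 7.5 also allows additional tests. A safety officer reviews reports as they occur (10.3.2). Dosing can be halted under 9.4 where "Based on AEs, laboratory findings, clinical findings or ECGs the Investigator or DSMB determine" that a safety review is needed. The Dosing paragraph of 3.B reports no safety or tolerability signal in the single-dose study, which included 30 g. All of this stands, and it makes the point a minor one. It does not cover a silent change that first appears after Day 21, because none of these provisions schedules a test that would find it. The single-dose experience is also a different exposure from 21 × 30 = 630 g over a period.

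A second reply is that Day -3 lies inside the washout, so a panel there does not cure the problem. That is correct, and the gain should be described as a shorter interval only.

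A reader might be tempted by four stronger readings, which the documents do not support:
- *That the drug-placebo comparison is biased.* Section 9.2 makes treatment comparisons within subject, and the laboratory schedule is the same on placebo and extract.
- *That these periods start with no safety check.* The Day -3 and Day 1 assessments contradict that; only the complete panel is missing.
- *That 54 of 81 measures risk.* It is simply every Period 2 and 3, and 18 of those starts are placebo.
- *That eligibility rests on stale laboratory results.* Section 6.2.1 says "Generally, all labs to assess entry criteria must be completed no less than 10 days before subject enters study". This may be lead time for review or a slip for a maximum. It names no upper limit, but no figure here depends on it. It is at most a separate wording clarification.

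**Conclusion.** The gap is real but small. Periods 2 and 3 begin with no complete chemistry and blood-count panel taken off study product, and 14 days pass between the last panel of one period and the first of the next. It affects 36 starts of extract, including all 18 at 30 g; the sharpest cases are the 18 that go directly from a lower to a higher extract dose, 12 of them to 30 g. What is lost is a check before each new treatment and the ability to place a Day 7 change in time. The documents give no basis for estimating how often such a change would occur.

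The counts assume full enrolment with all three periods completed, and a washout of exactly 7 days; a longer washout lengthens the gap. They also assume that the chemistry row of Figure 2 stands for the whole safety panel, since the figure has no separate row for blood counts. At screening the plan lists these together: "Blood samples will be taken for a complete blood chemistry, blood counts, thyroid hormone panel and urinalysis". This is a cheap improvement, not a flaw that threatens the study's conclusions.

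**What to change.** In Figure 2, mark the complete chemistry and blood-count panel at Day -3 for Periods 2 and 3, taken at the existing OGTT draw, and require its review before Day 1 dosing. In 9.6, name it as the reference for descriptive within-period laboratory change. Keep screening as the baseline for deciding whether a finding is an adverse event, so that an abnormality arising after Day 21 is still recorded and not absorbed into a new baseline.

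The cost is one mark in Figure 2, a sentence on review, a sentence in 9.6, 54 laboratory panels and slightly more blood at each of those draws. No visit, sample size or randomization changes. The review step needs results within 29 - 26 = 3 or 29 - 25 = 4 days. The sample is a during-washout sample, about 4-5 days after the last dose (3-6 with the window), and may carry residual effect. It shortens the unobserved interval before Day 7 from 14 days to about 9-10. A pre-dose Day 1 sample would follow the full washout, but it is an extra draw and may report after the first dose.
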